### 2 TRIAL OBJECTIVES AND ENDPOINTS

### 2.1 Objectives

### Primary objective

• To describe the efficacy of the Prepopik in children aged 9 years to 16 years for overall colon cleansing in preparation for colonoscopy based on the Aronchick scale by including oral polyethylene glycol (PEG) based preparation/local standard of care as a reference group

### **Secondary objectives**

- To describe the safety of Prepopik in children aged 9 years to 16 years through the collection of AEs, clinical laboratory tests, and physical examination
- To describe the completion of prep as directed to colon cleansing by Prepopik in preparation from colonoscopy in children aged 9 years to 16 years
- To describe the tolerability and satisfaction of colon cleansing by Prepopik in preparation for colonoscopy in children aged 9 years to 16 years as assessed by a standardized subject questionnaire administered at the study site before colonoscopy
- To evaluate pharmacokinetic (PK) characteristics of Prepopik in children aged 9 years to 16 years

#### 2.2 Endpoints

#### **Primary Endpoint**

• Proportion of subjects classified as success defined by "excellent" or "good" in the Aronchick scale

### **Secondary Endpoints**

- Incidence of adverse events and abnormal findings in clinical laboratory test and physical examination
- Proportion of subjects who took the assigned dose for the IMP
- Frequency of each category of the Tolerability and Satisfaction Questionnaire
- PK exposure will be assessed utilizing a sparse sampling of subjects (Sparse sampling means no need for special PK time)

Supersedes: 4
Page 19 of 65

#### 3 INVESTIGATIONAL PLAN

### 3.1 Overall Trial Design

This study is a randomized, assessor-blind, multicenter, dose-ranging study. Subjects undergoing an elective complete colonoscopy will randomly receive one of the following products:

- "Split Dose" Prepopik: 2 divided doses given the night before (first dose) and approximately 5 hours prior (second dose) to procedure. A dose is defined for one subset of subjects aged 9 years to 12 years as ½ sachet, for another subset of subjects aged 9 years to 12 years per randomization as 1 sachet and for subjects aged 13 to 16 years as 1 sachet. For "Day Before" Prepopik and fluids see Section 5.
- Oral PEG based preparation/local standard of care per appropriate label and/or institutional instructions.

Table 3-1 Overview of Study Treatment Groups by Age

	Age	Age Group		
Treatment Group	9-12 years	13-16 years	Total	
Prepopik: ½ sachet	15	0	15	
Prepopik: 1 sachet	15	15	30	
Standard of care	15	15	30	
Total subjects	45	30	75	

Pediatric subjects requiring colonoscopy, who fulfill all screening criteria, and sign an informed consent and assent (as required), will be randomized. One of the treatment arm products will be provided to the subject in a randomized fashion. The designated unblinded coordinator will instruct the subject and his/her parent/guardian on the use of the bowel preparation, and along with the subject and his/her parent/guardian, will sign a nondisclosure affidavit form (APPENDIX 1), which will prevent the subject and the unblinded coordinator from disclosing the bowel preparation treatment the subject used. Treatment will be blinded to the endoscopist and his/her assistant(s) assessing the efficacy of the 2 tested preparations when local or institutional methods are used. Their dosage timing and diet will be captured in the data. This approach had been used successfully in the Prepopik adult trials.

Colon cleansing will be performed using Prepopik for oral administration or oral PEG based preparation/local standard of care for oral solution.

Trial Code: 000103 Date: 28-Jul-2014 E-Protocol Amendment-18395; Ver. 5 Supersedes: 4

Page 20 of 65

Subjects randomized to the "Split Dose" Prepopik group will begin treatment ( $1^{st}$  dose) 1 day before colonoscopy between 5:00 and 9:00 PM, and will complete the treatment ( $2^{nd}$  dose)  $\geq 6$  hours after on the next day, and at least 5 hours prior but no later than 9 hours prior to colonoscopy. Additionally, if the subject is in the hospital, instructions will be written to follow as close as possible the aforementioned dosage schedule. Prepopik is reconstituted by mixing the powdered contents of the sachet in a cup with approximately 5 ounces of cold water. Following each administration of Prepopik, subjects will consume approximately five 8 ounce glasses of clear fluids after the first administration and at least three 8 ounce glasses of clear fluids after the second administration. For "Day Before" Prepopik and fluids see section 5.

Subjects randomized to the oral PEG based preparation/local standard of care will follow appropriate label and/or institutional instructions.

[figure not shown]
On the day before the procedure (24 hours prior), all subjects will be limited to a liquid diet only. Special meal instructions for diabetic subjects are provided in APPENDIX 2. The coordinator who dispenses the drug will instruct the subject and his/her parent/guardian about the exact requirements during the Randomization Visit (Visit 2).

Subjects will return to the site  $5 \pm 2$  days following their colonoscopy for a laboratory sample (chemistry, hematology and coagulation). Subjects/parents or guardians will have a telephone assessment on Day 28 after the colonoscopy procedure.

Efficacy of the tested preparations will be evaluated by an assessor-blinded endoscopist using the Aronchick scale for overall colon cleansing. A standardized subject questionnaire administered on the day of colonoscopy and prior to sedation and the procedure will assess tolerability and satisfaction of the product (to be filled out by the subject and/or guardian).

Supersedes: 4 Page 21 of 65

### 3.1.1 Trial Design Diagram

Subjects participating in PK subset will remain in the clinical research unit for needed blood draws at V2 and V3.

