#### **NUMBER OF SUBJECTS**

A sufficient number of subjects will be screened to ensure up to approximately 75 (for 9-12 years old, 15 subjects for the Prepopik ½ sachet x2, the Prepopik 1 sachet x2, and standard of care group; for 13-16 years old, 15 subjects for the Prepopik 1 sachet x2 and standard of care). For PK sampling, approximately 5 subjects per treatment group (a total of 15, 5 aged 13-16 years and 10 aged 9-12 years) will be assessed.

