### 3.2 Planned Number of Trial Sites and Subjects

Approximately 6-8 sites in the US are planned. A sufficient number of subjects will be screened to ensure up to approximately 75 (~15 subjects per treatment arm).

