# 7.3 Drug Concentration Measurements

For subjects that are participating in the PK subset, blood samples for measurement of picosulfate and magnesium plasma concentrations will be collected from approximately 15 subjects in the 3 Prepopik groups. Magnesium will be collected pre-dose at Visits 1, 2 or 3.). Picosulfate will be collected at Visit 3 (colonoscopy) in the (6-12 hour) window after the first dose of Prepopik. Sampling times at Visit 3 are at Hours 6, 8, and 12 for picosulfate concentrations and at Hour 10 for magnesium concentrations.

Analysis of the samples for sodium picosulfate and magnesium oxide will be performed by

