#### 8 ADVERSE EVENTS

#### **Adverse Event Definition** 8.1

An AE is any untoward medical occurrence in a subject participating in a clinical trial. It includes:

- Any unfavorable and unintended sign, symptom or disease temporally associated with the use of the IMP, whether or not considered to be caused by the IMP
- AEs commonly observed and AEs anticipated based on the pharmacological effect of the IMP
- Any laboratory abnormality, vital sign or finding from physical or gynecological examination assessed as clinically significant by the investigator (note: findings from assessments and examinations done during screening are not AEs, but are recorded as medical history.)
- Accidental injuries, reasons for any change in medication (drug and/or dose), reasons for any medical, nursing or pharmacy consultation, or reasons for admission to hospital or surgical procedures
- Overdoses and medication errors with and without clinical consequences

An adverse drug reaction (ADR) is an AE evaluated by the investigator as being probably or possibly causally related to treatment with the IMP.

A serious ADR is an SAE evaluated by the investigator and/or by Ferring as being probably or possibly causally related to treatment with the IMP (further described in Section 8.2.2).

An unexpected AE is an AE not identified in nature, severity, or frequency in the section "Undesirable Effects" in the sponsor's current Investigator's Brochure and current approved label.

A treatment-emergent AE is any AE that begins during the treatment period, or is a worsening of a pre-existing medical condition. The treatment period is the period during which a subject receives IMP.

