#### 8.2 **Collection and Recording of Adverse Events**

#### 8.2.1 **Collection of Adverse Events**

The investigator must monitor the condition of the subject throughout the trial from the time of obtaining informed consent until the last visit.

The sources of AEs cover:

- The subject's response to questions about his/her health (a standard non-leading question such as "How have you been feeling since your last visit?" is asked at each visit).
- Symptoms spontaneously reported by the subject.
- Investigations and examinations where the findings are assessed by the investigator to be clinically significant changes or abnormalities.

Trial Code: 000103 Date: 28-Jul-2014 E-Protocol Amendment-18395; Ver. 5

> Supersedes: 4 Page 39 of 65

• Other information relating to the subject's health becoming known to the investigator (e.g., hospitalization).

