10.2.2 Incidence of Adverse Events

The number and percentage of patients experiencing a specific TEAE, as well as the number of events reported, will be tabulated by SOC, preferred term, and treatment group, overall and by age group. Additional summary tables will be provided for AEs by maximum intensity and by relationship to study treatment. Additional summaries for related AEs, serious AEs, AEs leading to withdrawal, and AEs leading to death will be generated. Non-serious AEs with an incidence of 5% or greater in any treatment group will also be summarized.

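### About one third of each Prepopik arm, and no standard-of-care child, has a research-unit stay and extra PK blood draws after dosing; the TEAE tables should show this group separately as a supplement.

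*Protocol*

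**What the plan says.** **Who is sampled.** The synopsis (Number of Subjects) states that "approximately 5 subjects per treatment group (a total of 15, 5 aged 13-16 years and 10 aged 9-12 years) will be assessed". Protocol 7.3 limits this to Prepopik: samples "will be collected from approximately 15 subjects in the 3 Prepopik groups". No standard-of-care child is included.

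**What happens to them.** Protocol 3.1.1: "Subjects participating in PK subset will remain in the clinical research unit for needed blood draws at V2 and V3". Protocol 6.3 and the notes to Table 6-1 put the post-dose draws at Hours 6, 8, 10 and 12 after the first dose. The secondary-endpoint list in Protocol 2.2, however, describes the sampling as sparse and as needing no special PK time.

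**What counts as an AE.** Protocol 8.1: "An AE is any untoward medical occurrence in a subject participating in a clinical trial". Causation by the product is not required. Protocol 8.2.1 lists, besides the question put at each visit, "Symptoms spontaneously reported by the subject". SAP 10.2 treats any event that begins after the start of study treatment as treatment-emergent.

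**How AEs are tabulated.** SAP 10.2.2: "The number and percentage of patients experiencing a specific TEAE, as well as the number of events reported, will be tabulated by SOC", then by preferred term and treatment group, overall and by age group. SAP 6.4 defines a PK analysis set, but no AE table uses it. The additions listed in SAP 12 cover PK concentration summaries and not this split.

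**The concern.** PK participation is tied to treatment: one third of Prepopik children have it and no reference child does. Two routes can then add recorded events on one side only.

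- **Contact.** A child in the unit who vomits or feels dizzy is seen at once. A child at home has to report it later.
- **Procedure.** Bruising or fainting at a PK draw meets the AE definition and, because it starts after the first dose, is a TEAE.

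Both would be expected to raise the recorded Prepopik rate. Protocol 1.2 says that the safety of Prepopik will be compared with the PEG-based standard of care, and the TEAE tables set the groups side by side. With no formal test or model, those percentages are the safety result. A reader who sees an excess under Prepopik could not tell from the tables whether it comes from the preparation or from the PK sub-study.

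**Working it through.** **Inputs**

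- Arm size, Protocol 3.2: "A sufficient number of subjects will be screened to ensure up to approximately 75 (~15 subjects per treatment arm". Table 3-1 gives 3 × 15 = 45 Prepopik and 2 × 15 = 30 standard-of-care children.
- PK subset: 5 per Prepopik arm, 15 in total (synopsis).
- Split Dose first dose: 5:00 to 9:00 PM (Protocol 5.1). Draws at 6, 8, 10 and 12 hours (Protocol 6.3).
- Detection rates: none in the documents, so every value used below is an assumption.

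**The plan's own figure.** Protocol 9.1 gives an exact 95% CI of 65% to 90% for 80% success in 45 children. The Clopper-Pearson interval for 36/45 is 65.4% to 90.4%. The figure reproduces, and this point does not affect it.

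**Step 1: share with the extra contact.** 5/15 = 33% of each Prepopik arm and 15/45 = 33% overall, against 0/30 = 0% in standard of care.

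**Step 2: timing.** The earliest draw is at 17:00 + 6 h = 23:00 and the latest at 21:00 + 12 h = 09:00. The draws overlap the 6 to 10 hours that Protocol 1.1 gives for sodium picosulfate to act.

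**Step 3: effect on the recorded rate.** Let b be the proportion with a TEAE recorded outside the unit, taken as equal in both treatments. Let r be how many times as likely a PK child is to have one recorded.

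Prepopik rate = (10b + 5rb)/15 = b(2 + r)/3; standard-of-care rate = b.

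| b | r (assumed) | Prepopik | Standard of care |
|---|---|---|---|
| 20% | 1.5 | 23.3% | 20% |
| 20% | 2 | 26.7% | 20% |
| 30% | 1.5 | 35% | 30% |
| 30% | 2 | 40% | 30% |

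At b = 20% the excess over the expected 9 of 45 is 1.5 children (r = 1.5) or 3 children (r = 2).

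**Step 4: the same effect from a true rate.** Let p be the true rate in both treatments, s the detection outside the unit, and let detection inside be complete. Prepopik = p(2s + 1)/3; standard of care = ps. At p = 30%:

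| s (assumed) | Prepopik | Standard of care | Ratio |
|---|---|---|---|
| 90% | 28.0% | 27.0% | 1.04 |
| 75% | 25.0% | 22.5% | 1.11 |
| 50% | 20.0% | 15.0% | 1.33 |

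**Step 5: events caused by the draws.** If a proportion q of PK children has a draw-related TEAE and no other, Prepopik gains q/3. For an assumed q of 5% to 20% that is 1.7 to 6.7 points, and 0 in standard of care.

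**Step 6: common-event table.** SAP 10.2.2 also summarises non-serious AEs at 5% or more in any treatment group. One child in an arm of 15 is 1/15 = 6.7%, enough to cross that line.

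**Step 7: precision after a split.** Exact 95% CI at a 20% TEAE rate:

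| Group | All Prepopik | Outside the PK subset |
|---|---|---|
| Pooled | 9/45: 9.6% to 34.6% | 6/30: 7.7% to 38.6% |
| One arm | 3/15: 4.3% to 48.1% | 2/10: 2.5% to 55.6% |

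**The case against.** The strongest reply is that ascertainment is largely equal by design, and much of it stands.

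- AEs are scheduled at Visits 2 to 5 for every child (Table 6-1), with the same non-leading question.
- Visit 3 records AEs before and after colonoscopy, so under Split Dose the recall period is under a day.
- Every child is asked to complete the questionnaire on abdominal pain, fullness, waking and nausea, and it is tabulated by arm.
- Every child has blood drawn at Visits 3 and 4, so the difference is up to four more draws and not draws against none.
- The Visit 2 PK sample is a pre-dose baseline and cannot produce a TEAE.
- Draw-related events would probably be judged unrelated, and SAP 10.2.2 already tabulates by relationship.

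The unit stay also rests on one sentence in Protocol 3.1.1. Overnight observation follows from the dose and draw times but is not stated. Protocol 3.1 provides for subjects in hospital, so some children outside the subset may be observed too.

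Further, safety is descriptive, no between-arm AE test is planned, and the excess in Step 3 at b = 20% lies inside the sampling error of 45 children. AE and PK listings by subject would let a reader rebuild the split. That is possible, but a planned table avoids a post hoc explanation.

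A reader might go further and conclude that comparative safety is a stated secondary objective. It is not: the reference group is named in the primary, efficacy objective. The comparison of safety appears only in the rationale (Protocol 1.2).

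**Conclusion.** The point holds as a limited one. The documents establish that PK participation is confined to Prepopik, covers about a third of each Prepopik arm, and brings extra contact and draws after dosing that the TEAE tables do not separate. That this adds recorded events is an inference. Its likely direction is against Prepopik; its size cannot be obtained from the documents, and the figures above only show what assumed detection ratios would do.

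Three stronger readings are not supported.

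- A reader might infer that Prepopik AEs are sought under a different schedule. They are not; the scheduled contacts are identical.
- A reader might take the 20% and 30% in Step 3 as true rates. They are rates recorded outside the unit. If the truth were 20% and standard of care recorded 20%, detection there would already be complete, and better observation alone could add nothing.
- A reader might conclude that between-arm statements should rest only on children outside the PK subset, or that sampling-related AEs should leave the totals. The first drops a third of the Prepopik safety data for a subset whose selection is not described as randomized. The second conflicts with the AE and TEAE definitions.

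**What to change.** In SAP 10.2.2, before database lock:

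1. Keep the full TEAE tables, with all TEAEs and all children in the safety set, as the main presentation.
2. Add one supplementary TEAE incidence table with Prepopik children split by PK participation (yes/no) beside standard of care. Label it a sensitivity view, because the documents do not describe selection into the PK subset as randomized.
3. Flag AEs that the investigator attributes to PK sampling, in tables and listings, without removing them from the totals.

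Separately, reconcile the statement in Protocol 2.2 that no special PK time is needed with the unit stay in 3.1.1 and the timed draws in 6.3.

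**Cost.** One more table and one flag. PK membership is already known from the PK analysis set (SAP 6.4). The supplementary groups are smaller, about 30 Prepopik children outside the subset, with the wider intervals shown in Step 7. The main table loses nothing.

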#### 3.1.2 Trial Schedule

First patient first visit is estimated for October 2013 and last patient last visit is expected in May 2015. The expected overall duration of the trial will be approximately 20 months.

Trial Code: 000103 Date: 28-Jul-2014 E-Protocol Amendment-18395; Ver. 5

Supersedes: 4 Page 22 of 65

### 3.2 Planned Number of Trial Sites and Subjects

Approximately 6-8 sites in the US are planned. A sufficient number of subjects will be screened to ensure up to approximately 75 (~15 subjects per treatment arm).

### 3.3 Interim Analysis

No interim analysis is planned.

### 3.4 Data Monitoring Committee (DMC)

No DMC will be established for this study.

### 3.5 Discussion of Overall Trial Design and Choice of Control Groups

#### 3.5.1 Trial Design

The study design is assessor-blinded and randomized. Blinding treatment to the endoscopist and his/her assistant(s) assessing the efficacy of the tested preparations removes possible bias. A placebo-controlled design would not be practical or ethical in this study as subjects would be required to have a second colonoscopy.

### 3.5.2 Selection of Endpoints

The primary endpoint, overall colon cleansing prior to colonoscopy, will be assessed by a blinded assessor endoscopist using the Aronchick scale. The Aronchick scale is a validated instrument that has been widely used and universally accepted, and has been previously used in pivotal trials that led to new drug application (NDA) approval, including the approval of HalfLytely. However, this study will compare Prepopik to oral PEG local standard of care preparations. Essentially, each endoscopic center has its own preparation concoction based on some combination of diet PEG 3350 sports drinks, enemas and stimulant laxatives.

Each investigational site will be trained on the use of the Aronchick Scale both at the investigator meeting and at initial site visit; subjects will not be initiated until all assessing gastroenterologists involved in the study at the investigational site are confident in using this tool.

#### 3.5.3 Blinding / Unblinding

#### Blinding

The study treatment(s) will be allocated according to computer-generated randomization codes prepared for all study sites. Treatment is blinded to the endoscopist and his/her assistant(s) performing the colonoscopy and assessing the efficacy of the tested preparations.

Prior to the start of the study, the investigator will assign a coordinator to act as the unblinded coordinator. This person will be responsible for distribution and accountability of the drug. The unblinded coordinator will instruct each subject as to the proper administration and the timing of the drug administration. This person will be available to answer the subject's and parent's/guardian's questions regarding the study drug and its administration.

Trial Code: 000103 Date: 28-Jul-2014 E-Protocol Amendment-18395; Ver. 5

> Supersedes: 4 Page 23 of 65

The integrity of blinding will be further preserved by requiring each subject or parent/guardian and the unblinded coordinator to sign a nondisclosure affidavit form instructing subjects/parents/guardians and the unblinded coordinator not to disclose the treatment groups to the endoscopist performing the colonoscopy and his/her assistants.

### Unblinding of Individual Subject Treatment

In case of an emergency, the emergency decoding envelope will be available to the investigator and the sponsor's medical officer. Breaking of the blind in individual subjects is only permitted in case of a serious, unexpected or other important AE, when the knowledge of the investigational product in question is required for therapeutic decisions for the management of the subject.

If it is necessary to unblind an individual subject's treatment for the purposes of expedited reporting to the authorities, only those individuals within Ferring Pharmaceuticals whose responsibility it is to report this information will know the identity of the IMP. Every attempt will be made to ensure that all other study and site personnel will continue to remain blinded throughout the course of the study.

As far as the emergency permits, the need to break the blind will be agreed by the investigator and the sponsor. It should be recorded in the CRF that the blind is broken, why, when, and by whom.

In case of accidental unblinding (e.g., the subject tells the assessor), the same documentation as for emergency unblinding must be obtained, i.e., the code envelope must be opened and why, when, and by whom must be noted both on the code envelope and in the CRF, and the event must also be recorded in the subject's medical record.

It may be necessary to unblind an individual subject's treatment for the purposes of expedited reporting to the authorities and/or IRBs. In that situation, every effort will be made to maintain blinding of sponsor personnel involved in data analysis and interpretation. Other personnel may be unblinded for suspected unexpected serious adverse reactions, including trial site staff as well as staff acting on behalf of Ferring.

Information on whether the blind has been broken for any subjects must be collected before the database is declared clean and is released to the statistician.

